## **Number of centers & patients**

Multicenter study with subject number = 40

**Population****Inclusion criteria**

- Confirmed diagnosis of MS (no sub-type restrictions)
- Age  $\geq 18$
- No change in disease modifying therapy in 60 days
- Patient willing and able to complete micturition diary
- Urinary urgency (8 or more entries of bladder urgency score  $\geq 2$ ) in 72hr voiding diary recorded during screening period
- Micturition frequency  $\geq 8$  / day or incontinence  $\geq 2$  episodes in 72hr voiding diary recorded during screening period
- At least 36 hours of voiding activity recorded in 72 hour voiding diary recorded during screening period
- Non-antimuscarinics medications that are likely to influence bladder function may not be initiated between screening and study completion. They may be continued with no dose changes during the study.
- Discontinued use of antimuscarinics at least two weeks prior to screening
- Able to give informed consent

**Exclusion criteria**

- Females who are breast-feeding, pregnant or have potential to become pregnant during the course of the study (fertile and unwilling/unable to use effective contraceptive measures).
- MS exacerbation within 30 days of screening
- Cognitive deficits that would interfere with the subject's ability to give informed consent or perform study testing.
- Screening blood pressure  $> 165$  systolic or 100 diastolic
- History of allergy to Mirabegron.
- Screening post-void residual  $> 200$ ml
- Evidence of urinary tract infection at screening
- Evidence of chronic inflammation such as interstitial cystitis, bladder stones, previous pelvic radiation therapy, or previous or current malignant disease of the pelvic organs
- Intravesical botulinum toxin treatment within the previous six months of screening.
- Presence of InterStim device
- Use of indwelling catheter or self-catheterization
- Concurrent use of thioridizine, flecainide, propafenone or Digoxin
- Concurrent use of antimuscarinics: oxybutynin (Ditropan®, Ditropan XL ®), tolterodine (Detrol®, Detrol LA®), fesoterodine extended-release (Toviaz®), solifenacin (Vesicare®), trospium (Sanctura®, Sanctura XR®), darifenacin extended release (Enablex®)
- Screening estimated glomerular filtration rate (eGFR)  $< 60$ , AST or ALT  $> 2x$  upper limit of normal
- Any other serious and/or unstable medical condition

**Behavioral Modification with Pelvic Floor Exercise (BM-PFE) Educational Material**

We will utilize a 20 minute presentation, written by a physical therapist, utilizing a power point presentation. Slides will include images such as pelvic floor anatomy as well as

---

outlines of key points. Participants will be given a paper copy of the power point presentation to take home for reference and to help them with a home bladder exercise regimen.

The following topics are part of this power point presentation:

- Bladder health: What's normal?
- Bladder dietary irritants
- Bladder retraining and urge delay techniques
- Pelvic floor anatomy and function
- How to perform a "Kegel"
- "Kegel" home exercise program
- Pelvic floor exercises with functional activities
- Maintaining your home exercise program

Subjects will have the opportunity to ask the study physician follow-up questions as needed.

### **Investigational drug**

The study medication and matching placebo will be provided by Astellas Pharma Inc. The active medication will be mirabegron (MBG) 25mg po daily from Baseline Visit to Titration Visit. At the Titration Visit subjects will be asked to choose to up-titrate to 50mg (or matching placebo) or to continue at 25mg dose (or matching placebo), while remaining blinded to treatment. The research pharmacist will dispense the active or placebo medication at randomization and again at the Titration Visit. An extra 5 day supply of medication will be provided for each study period to allow a window for scheduling of appointments.

### **Randomization**

- Randomization will occur at the research pharmacy of EvergreenHealth (EH).
- Non-EH research sites will submit a randomization request to the EH Research Pharmacist.
- EH Research Pharmacist will assign randomization to placebo vs. active drug and record in randomization code book.
- EH Research Pharmacist will send the randomization assignment (placebo or active drug assignment) back to un-blinded staff at the enrolling site.
- Un-blinded staff at the enrolling site will dispense medication based on EH provided randomization assignment.
- The investigating physician, nurse and research coordinator will be blinded as to treatment arm until the code is broken. The randomization code may be broken by the investigator only in a medical emergency. The reasons for this have to be documented carefully.

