## Protocol Summary

STUDY DRUG	Mirabegron 25-50mg daily
TITLE	Pilot study of mirabegron and behavioral modification including pelvic floor exercise for overactive bladder in multiple sclerosis ( MIRROR )
STUDY OVERVIEW	
A multi-center, randomized 1:1 placebo controlled 10-week study of mirabegron as add-on therapy to an educational intervention on behavioral modification including pelvic floor exercise (BM-PFE) to a cohort of 40 MS subjects with overactive bladder (OAB).
 
Active drug will be mirabegron 25mg daily with optional up-titration to 50mg daily after approximately 5 weeks. Subjects will be randomized at the Baseline Visit based on recordings in a voiding diary kept for 72 continuous hours in the screening period.
 
Voiding diaries of a 72 hour period each will be utilized during the screening period, between Phone Visit 1 and Titration and between Phone Visit 2 and Final Visit. In the diaries, subjects will record the time of each micturition and/or urgency episode, urine volume with each void (when available), any episode of incontinence, and the severity of urgency (Overactive Bladder Symptom Composite Score, OAB-SCS): 1 = no urgency (normal voiding); 2 = mild (could postpone voiding for as long as necessary without fear of incontinence); 3 = moderate (could postpone voiding for a short while without fear of leakage); 4= severe (could not postpone, had to rush to the toilet); 5= urgency incontinence (could not make it to the toilet without some leakage) Each voiding event is multiplied by the score for the event and then all events are summed to generate a total daily OAB-SCS cumulative score).
 
Primary outcome will be average daily OAB-SCS total score, Final Visit vs. Baseline. This accounts for the frequency, urgency and incontinence components of OAB.

RATIONALE	This design will demonstrate the effects of behavioral modification, including pelvic floor exercise on OAB through the placebo arm of the study. Adding mirabegron may yield greater results than BM-PFE alone. The standard starting dose is 25mg daily. An optional up-titration to 50mg is included, since some patients may respond better to the higher dosage. This titration will occur at about 5 weeks to allow a balanced period of time for recording response to the two dosages.
STUDY HYPOTHESIS	Treatment with Mirabegron will improve urinary urgency control beyond that achieved with pelvic floor exercises alone.

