STUDY SUBJECTS	40 subjects with multiple sclerosis and OAB complaints.
DESIGN	Multiple-dose, randomized, placebo-controlled prospective, single-site, investigator-initiated trial.
DURATION OF STUDY	Approximately 10 weeks (active treatment)

TREATMENT REGIMEN	
Group A will receive Mirabegron 25mg daily      Group B will receive placebo      Group A and B will receive the same baseline education in pelvic floor exercise based on viewing of an instructional presentation plus take-home printed material.

TRIAL PERIODS	
Screening Period
 
 
• Screening to Baseline
 
 
Treatment Period
 
 
• Baseline to Final Visit (or Study Drug Discontinuation), includes Baseline, Phone Visit 1, Titration Visit, Phone Visit 2 and Final Visit
 

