	
 
Concurrent use of thioridazine (Mellaril® or Mellaril-S®), flecainide (Tambocor®), propafenone (Rythmol®) or digoxin (Lanoxin®)
 
Concurrent use of antimuscarinics: oxybutynin (Ditropan®, Ditropan XL®), tolterodine (Detrol®, Detrol LA®), fesoterodine extended-release (Toviaz®), solifenacina (Vesicare®), trospium (Sanctura®, Sanctura XR®), darifenacina extended release (Enablex®)
 
Screening estimated glomerular filtration rate (eGFR) < 60, AST or ALT > 2x upper limit of normal
 
Any other serious and/or unstable medical condition
 

NO. OF SUBJECTS	N= 40. This will include 20 subjects taking mirabegron and 20 subjects taking placebo.
EFFICACY (Outcome measures)	
Primary Outcome Measure:
 
 
Primary outcome will be Average daily OAB-SCS total score, Baseline vs. Final Visit
 
 
Secondary Outcome Measures based on voiding diary, compared to Baseline:
 
 
Titration Visit: Average daily OAB-SCS total score
 
Titration and Final Visit: A) mean # of micturitions/day; B) Mean number of incontinence episodes/day; C) Mean volume voided/micturition
 
 
Secondary Outcome Measures based on the following assessments at Titration Visit and Final Visit compared to Baseline:
 
 
Qualiveen Questionnaire
 
Subject Global Impression (single question)
 
PFE adherence question
 
Bladder Management Difficulties Questionnaire – Short Form (SCI-QOL v1.0)
 
 
Exploratory Outcome Measures based on the following assessments at Titration Visit and Final Visit compared to Baseline:
 
 
Bowel Management Difficulties Questionnaire – Short Form (SCI-QOL v1.0)
 

STATISTICAL METHODS	See Statistics section

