Pelvic floor rehabilitation has a well-established role in the management of stress incontinence and idiopathic OAB. There is some evidence that pelvic floor exercise taught by physiotherapists over multiple sessions improves OAB in MS. However, access to pelvic floor physical therapy is limited by third-party payer coverage, availability of therapists with the necessary expertise and incurred expenses and time requirements for the patients. Behavioral modification, including pelvic floor exercise (BM-PFE) may be provided in a clinical setting using relevant educational materials. The BM-PFE component will offer an important educational benefit to all subjects interested in this study. Our center has a strong pelvic rehabilitation program with three therapists who are well-suited to produce the educational component of this study.

Adding MGB may yield greater results than BM-PFE alone. The standard starting dose is 25mg daily. An optional up-titration to 50mg is proposed, since some patients may respond better to the higher dosage, based on a Phase III trial including 25mg and 50mg daily treatment arms. This titration will occur at visit 3; 32-40 days post Baseline Visit, to allow a balanced period of time for recording response to the two dosages. Both dosages have been reported to be effective in treating OAB within 12 weeks.

This study explores the benefits of combining a brief BM-PFE educational program with a pharmacotherapy, MBG for OAB due to MS. Our objective is to determine the effect of BM-PFE with and without MBG in reducing the OAB Symptom Composite Score (OAB SCS). The OAB SCS is a validated measure that incorporates urinary frequency, urgency and incontinence episodes. The study design will also test differences in efficacy and tolerability between 25mg and 50mg doses of MBG.

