## Statistical Analysis

Demographics and baseline disease characteristics, including age, gender, MS type and duration of disease, level of disability (EDSS), and disease modifying therapy status will be compared between study groups.

Summary and analysis of primary and secondary outcome measures will include

1. Summary statistics (n, mean, standard deviation, median, minimum and maximum) at baseline and week 5 and week 10 by treatment
2. Summary of % change from baseline to week 5 and 10.
3. Significance testing

For the primary outcome measure, Average daily OAB-SCS, each voiding event is multiplied by the score for the event and then all events are summed to generate a total daily OAB-SCS cumulative score. Each daily total score is averaged to generate the Average daily OAB-SCS total score. For incomplete days (e.g. went out for 6 hours and forgot to record voids) the sum score will be adjusted as follows: total score over 24 hours X 24 / actual # of hours included in documentation (see reference Zinner et al).

Mean OAB-SCS score at Baseline Visit will be included in the model as an independent variable. The primary time points for all comparative measures will be Baseline Visit, Titration Visit and Final Visit. Outcome measures will be compared between groups using analysis of covariance (ANCOVA) or other method. Demonstration of superiority will depend on achieving statistical significance for the primary endpoint. Level of significance will be defined as  $p=0.05$ . All statistical tests will be two-sided. Statistical assistance will be provided by a statistician consultant whose company is contracted with EvergreenHealth and whose services we have used on two recent MS studies.

Aggregate, de-identified data from the Bladder and Bowel Management Difficulties Short Form Questionnaires (SCI-QOL v1.0) will be shared with the University of Washington in Seattle, WA. This will be done as a courtesy for giving the investigator permission to use these questionnaires in this protocol.

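### Patients are randomised at several sites, but site appears in neither the stated allocation method nor the named ANCOVA, so chance site-arm imbalance in 40 patients goes uncorrected

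*Combined protocol and SAP*

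**What the plan says.** **Number of sites.** The Protocol Summary (study overview) describes "A multi-center, randomized 1:1 placebo controlled 10-week study of mirabegron", and the section Number of centers & patients says "Multicenter study with subject number = 40". The Randomization section adds that "Non-EH research sites will submit a randomization request to the EH Research Pharmacist", and the Enrollment section refers to participating centres in the plural. Against these, the design row of the Protocol Summary reads "Multiple-dose, randomized, placebo-controlled prospective, single-site, investigator-initiated trial". Neither the number of sites nor the expected enrolment per site is given.

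**Allocation.** The ratio is 1:1, with "N= 40. This will include 20 subjects taking mirabegron and 20 subjects taking placebo". The Randomization section sets out who assigns, records, transmits and dispenses. The assignment step itself is: "EH Research Pharmacist will assign randomization to placebo vs. active drug and record in randomization code book". No method of generating the sequence, block, stratum or minimisation factor is named. Each assignment goes back, unmasked, to un-blinded staff at the enrolling site.

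**Analysis.** The Statistical Analysis section states: "Mean OAB-SCS score at Baseline Visit will be included in the model as an independent variable". No other covariate is named. The method is ANCOVA or an unspecified alternative, and site is not among the baseline characteristics to be compared between groups.

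**The concern.** In a trial of 40 patients, an unstratified sequence can easily put noticeably more of one site's patients in one arm. If sites differ in outcome, part of that difference enters the treatment estimate, and a model with baseline score alone does not take it out.

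There are reasons to think that sites could differ. Both arms receive the behavioural and pelvic floor programme, and the Protocol Summary expects the placebo arm to show its effect. The Background section says of the lead centre: "Our center has a strong pelvic rehabilitation program with three therapists who are well-suited to produce the educational component of this study". Follow-up questions about the exercises go to the study physician. Study staff give the diary and void-volume training, and the diary produces the primary outcome. Adjusting for the baseline score deals with site differences in starting severity, but not with differences in response to the programme or in diary recording.

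The result also has a formal use: the Statistical Analysis section makes a superiority claim depend on the primary endpoint being significant at 0.05, two-sided.

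**Working it through.** **Inputs from the documents:** N = 40, 1:1, 20 per arm; baseline OAB-SCS as the only named covariate; two-sided 0.05.

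**Assumed, because the documents give no figure:** patients enrolled outside the lead site, n = 6 to 20; site difference in outcome, 0.2 to 0.5 SD.

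**1. The plan's own figure.** 40 at 1:1 gives 20/20, as stated. No effect size, SD, power or dropout is given, so there is no sample-size calculation to reproduce.

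**2. Unequal arm totals.** Relative efficiency is 4·n1·n2/N². At 22/18 it is 4·22·18/1600 = 0.99. At 24/16 it is 4·24·16/1600 = 0.96. The loss is small.

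**3. Site mix with arms fixed at 20/20.** Suppose the non-lead sites enrol n patients, of whom k fall in the mirabegron arm. With no stratification by site, k is hypergeometric (40 patients, 20 on mirabegron, n drawn). The lead-site share differs between arms by |2k − n|/20. A gap of at least 20 points means |2k − n| ≥ 4; at least 30 points means |2k − n| ≥ 6.

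For n = 10, a 20-point gap needs k ≤ 3 or k ≥ 7. The lower tail is 0.0002 + 0.0040 + 0.0282 + 0.1043 = 0.1367, and doubling it gives 0.273.

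| Non-lead enrolment (assumed) | P(gap ≥ 20 points) | P(gap ≥ 30 points) |
|---|---|---|
| 6 | 18.2% | 2.0% |
| 8 | 23.5% | 4.4% |
| 10 | 27.3% | 6.5% |
| 12 | 30.1% | 8.2% |
| 20 | 34.3% | 11.3% |

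**4. Effect on the estimate.** If site is left out of the model, the shift is the gap times the site difference. At 20 points it is 0.20 × 0.2 = 0.04 SD to 0.20 × 0.5 = 0.10 SD. At 30 points it is 0.30 × 0.2 = 0.06 SD to 0.30 × 0.5 = 0.15 SD. The standard error of an unadjusted difference with 20 per arm is √(1/20 + 1/20) = 0.316 SD. The shift is therefore about 0.04/0.316 = 0.13 to 0.15/0.316 = 0.47 of a standard error.

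**5. Cost of a two-level site factor.** Error df with intercept, treatment and baseline is 40 − 3 = 37; with site it is 36. The two-sided 5% critical t goes from 2.026 to 2.028.

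**6. Cost of stratified blocks.** With blocks of 4 and 6, an unfinished block leaves a stratum at most 3 apart. Two strata are then at most 6 apart overall, 23/17 at worst, where relative efficiency is 4·23·17/1600 = 0.98.

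**The case against.** **The documents do not prescribe simple randomisation.** A reader might infer that the plan tosses a coin for each patient, so that an exact 20/20 has a probability of only 12.5% (C(40,20)/2⁴⁰). The text does not support this. It is silent on the method, and a stated 20/20 with a central pharmacist and a code book fits a restricted list equally well. This objection stands in full, which is why the working fixes the arms at 20/20.

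**The evidence for a site effect is thin.** The teaching is one standard 20-minute presentation with a paper copy, and both groups receive the same education. The Background sentence about the therapists concerns producing the material, not delivering it at one centre. Baseline adjustment will absorb much of any difference in severity. This stands too: site is a plausible prognostic factor, not a demonstrated one.

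**Chance imbalance is not bias.** Over repeated randomisations the shift averages zero, and a valid test does not require stratification or a site term. That is right. The argument for acting is that this is avoidable error in one small trial, and that avoiding it costs almost nothing.

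**Blocking within site has a risk of its own.** Un-blinded staff at the enrolling site see each assignment. In a block of 2 the second assignment follows from the first. Short blocks should therefore not be used, and block sizes must be withheld from those staff as well.

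**Conclusion.** The point holds as a low-cost improvement. Several sites enrol, the allocation method is not specified, and the named model has no site term. With arms of 20/20 and no stratification by site, a gap of at least 20 points in lead-site share has probability 18% to 34% for non-lead enrolment of 6 to 20. A gap of at least 30 points has probability 2% to 11%. With an assumed site difference of 0.2 to 0.5 SD, gaps of 20 to 30 points move the estimate by 0.04 to 0.15 SD if site is left out. Site numbers and the size of any site effect are assumptions; if sites do not differ, nothing is lost by leaving site out.

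Two stronger conclusions might be drawn, and neither is supported. One is that unequal arms threaten the trial's precision: 24/16 keeps 96% of the efficiency. The other is that the trial is biased as planned: the error is random and averages zero. The single-site wording is a contradiction to be reconciled. The operational text in Randomization and Enrollment describes several sites.

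**What to change.** 1. **Statistical Analysis:** name site as a factor in the primary ANCOVA, beside baseline OAB-SCS. Use two levels, EvergreenHealth versus other sites, if the other sites are small.
2. **Randomization:** state that a computer-generated list is prepared in advance and held by the EvergreenHealth research pharmacist, in permuted blocks stratified by the same two-level factor. Block sizes should vary at random (for example 4 and 6, not 2) and be concealed from all site staff, including the un-blinded dispensing staff.
3. **Protocol Summary, design row:** reconcile the single-site wording with the study overview and with the sections Number of centers & patients, Randomization and Enrollment.

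The cost is a new list at the pharmacy, one model term and one error degree of freedom. Unfinished blocks may leave the totals a few patients off 20/20, which is a negligible loss. If randomisation has already begun, the method actually used can be documented and the site factor can still be prespecified before unblinding.

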### **Concomitant therapy**

All concomitant therapy will be documented. Prohibited will be concurrent use of antimuscarinics listed in Appendix 3: oxybutynin (Ditropan®, Ditropan XL ®), tolterodine (Detrol®, Detrol LA®), fesoterodine extended-release (Toviaz®), solifenacina (Vesicare®), trospium (Sanctura®, Sanctura XR®), and darifenacina extended release (Enablex®) within the previous 2 weeks of screening. Also prohibited will be concurrent use of thioridazine, flecainide, propafenone or Digoxin and intravesical botulinum toxin treatment within the

---

previous six months. Medications that are likely to influence bladder function may not be initiated between screening and study completion. They may be continued with no dose changes during the study. This is listed as Appendix 3 and includes anticholinergic medications and drugs used in treatment of benign prostatic hypertrophy.

### **Interruption or discontinuation of treatment**

Every patient has the right to discontinue study participation at any time, and every patient may be discontinued from the study by the PI for any reason beneficial to his/her wellbeing or any other reason. All data generated up to the time of discontinuation from the study will be analyzed and the reason(s) for discontinuation will be recorded.

### **Treatment Compliance**

Patients will be asked to return all unused medication and all medication bottles, including empty bottles, at each visit and at the end of the study and the quantity of returned medication will be documented.

### **Blinding**

The subjects will receive identical appearing active or placebo study medication tablets, with identification known only to the research pharmacist.

